5.3.5.6 Abnormal Vital Sign Values

Not every vital sign abnormality qualifies as an AE. A vital sign result must be reported as an AE if it meets any of the following criteria:

- Is accompanied by clinical symptoms
- Results in a change in study treatment (e.g., treatment interruption or treatment discontinuation)

- Results in a medical intervention or a change in concomitant therapy
- Is clinically significant in the investigator's judgment

It is the investigator's responsibility to review all vital sign findings. Medical and scientific judgment should be exercised in deciding whether an isolated vital sign abnormality should be classified as an AE.

If a clinically significant vital sign abnormality is a sign of a disease or syndrome (e.g., high blood pressure), only the diagnosis (i.e., hypertension) should be recorded on the AE eCRF.

Observations of the same clinically significant vital sign abnormality from visit to visit should only be recorded once on the AE eCRF (see Section 5.3.5.4 for details on recording persistent AEs).

5.3.5.7 Abnormal Liver Function Tests

The finding of an elevated ALT or AST ($>3 \times ULN$) in combination with either an elevated total bilirubin ($>2 \times ULN$) or clinical jaundice in the absence of cholestasis or other causes of hyperbilirubinemia is considered to be an indicator of severe liver injury (as defined by Hy's Law). Therefore, investigators must report as an AE the occurrence of either of the following:

- Treatment-emergent ALT or AST $>3 \times ULN$ in combination with total bilirubin $>2 \times ULN$ (of which $\geq 35\%$ is direct bilirubin)
- Treatment-emergent ALT or AST $>3 \times ULN$ in combination with clinical jaundice

The most appropriate diagnosis (if a diagnosis cannot be established) of the abnormal laboratory values should be recorded on the AE eCRF (see Section 5.3.5.2) and reported to the Sponsor immediately (i.e., no more than 24 hours after learning of the event), either as a SAE or an AESI (see Section 5.4.2).

5.3.5.8 Deaths

All deaths that occur during the protocol-specified AE reporting period (see Section 5.3.1), regardless of relationship to study drug, must be recorded on the AE eCRF and immediately reported to the Sponsor (see Section 5.4.2). This includes death attributed to progression of MS.

Death should be considered an outcome and not a distinct event. The event or condition that caused or contributed to the fatal outcome should be recorded as the single medical concept on the AE eCRF. Generally, only one such event should be reported. If the cause of death is unknown and cannot be ascertained at the time of reporting, "unexplained death" should be recorded on the AE eCRF. If the cause of death later becomes available (e.g., after autopsy), "unexplained death" should be replaced by the established cause of death. The term "sudden death" should not be used unless combined with the presumed cause of death (e.g., "sudden cardiac death").

If the death is attributed solely to progression of MS, "Multiple Sclerosis progression" should be recorded on the AE eCRF.

Deaths that occur after the AE reporting period should be reported as described in Section 5.6.

5.3.5.9 Pre-existing Medical Conditions

A pre-existing medical condition is one that is present at the screening visit for this study. Such conditions should be recorded on the General Medical History and Baseline Conditions eCRF.

A pre-existing medical condition should be recorded as an AE only if the frequency, severity, or character of the condition worsens during the study. When recording such events on the AE eCRF, it is important to convey the concept that the pre-existing condition has changed by including applicable descriptors (e.g., "more frequent headaches").

5.3.5.10 Lack of Efficacy or Worsening of Multiple Sclerosis

Events that are clearly consistent with the expected pattern of progression of the underlying disease should not be recorded as AEs. These data will be captured as efficacy assessment data only. In most cases, the expected pattern of progression will be based on components of cCDP: EDSS scores and/or T25FWT scores and/or 9-HPT times (Section 2.1.1). In rare cases, the determination of clinical progression will be based on symptomatic deterioration. However, every effort should be made to document progression through use of objective criteria. If there is any uncertainty as to whether an event is due to disease progression, it should be reported as an AE.

5.3.5.11 Hospitalization or Prolonged Hospitalization

Any AE that results in hospitalization (i.e., inpatient admission to a hospital) or prolonged hospitalization should be documented and reported as a serious AE (per the definition of SAE in Section 5.2.2), except as outlined below.

An event that leads to hospitalization under the following circumstances should not be reported as an AE or a SAE:

- Elective hospitalizations or surgical procedures that are a result of a patient's pre-existing condition(s) that have not worsened since receiving trial medication. Examples may include, but are not limited to, cholecystectomy for gallstones, and diagnostic testing. Such events should still be recorded as medical procedures in the concomitant procedures/treatments eCRF.
- Hospitalization to receive trial medication such as infusions of ocrelizumab unless this is prolonged (more than 24 hours).
- Hospitalization following an MS relapse as long as the reason for hospitalization is to receive standard treatment with IV methylprednisolone

An event that leads to hospitalization under the following circumstances is not considered to be a SAE, but should be reported as an AE instead:

- Hospitalization that was necessary because of patient requirement for outpatient care outside of normal outpatient clinic operating hours

5.3.5.12 Cases of Accidental Overdose or Medication Error

Accidental overdose and medication error (hereafter collectively referred to as "special situations"), are defined as follows:

- Accidental overdose: accidental administration of a drug in a quantity that is higher than the assigned dose
- Medication error: accidental deviation in the administration of a drug

In some cases, a medication error may be intercepted prior to administration of the drug.

Special situations are not in themselves AEs but may result in AEs. Each AE associated with a special situation should be recorded separately on the AE eCRF. If the associated AE fulfills seriousness criteria, the event should be reported to the Sponsor immediately (i.e., no more than 24 hours after learning of the event; see Section 5.4.2). For ocrelizumab, AEs associated with special situations should be recorded as described below for each situation:

- Accidental overdose: Enter the AE term. Check the "Accidental overdose" and "Medication error" boxes
- Medication error that does not qualify as an overdose: Enter the AE term. Check the "Medication error" box
- Medication error that qualifies as an overdose: Enter the AE term. Check the "Accidental overdose" and "Medication error" boxes

In addition, all special situations associated with ocrelizumab, regardless of whether they result in an AE, should be recorded on the AE eCRF as described below:

- Accidental overdose: Enter the drug name and "accidental overdose" as the event term. Check the "Accidental overdose" and "Medication error" boxes.
- Medication error that does not qualify as an overdose: Enter the name of the drug administered and a description of the error (e.g., wrong dose administered, wrong dosing schedule, incorrect route of administration, wrong drug, expired drug administered) as the event term. Check the "Medication error" box.
- Medication error that qualifies as an overdose: Enter the drug name and "accidental overdose" as the event term. Check the "Accidental overdose" and "Medication error" boxes. Enter a description of the error in the additional case details.
- Intercepted medication error: Enter the drug name and "intercepted medication error" as the event term. Check the "Medication error" box. Enter a description of the error in the additional case details.

As an example, an accidental overdose that resulted in a headache would require two entries on the AE eCRF, one entry to report the accidental overdose and one entry to report the headache. The "Accidental overdose" and "Medication error" boxes would need to be checked for both entries.

5.3.5.13 Patient-Reported Outcome Data

AE reports will not be derived from PRO data by the Sponsor. Sites are not expected to review the PRO data for AEs.

5.3.5.14 Safety Biomarker Data

AE reports will not be derived from safety biomarker data by the Sponsor, and safety biomarker data will not be included in the formal safety analyses for this study. In addition, safety biomarker data will not inform decisions on patient management.

5.4 IMMEDIATE REPORTING REQUIREMENTS FROM INVESTIGATOR TO SPONSOR

Certain events require immediate reporting to allow the Sponsor to take appropriate measures to address potential new risks in a clinical trial. The investigator must report such events to the Sponsor immediately; under no circumstances should reporting take place more than 24 hours after the investigator learns of the event. The following is a list of events that the investigator must report to the Sponsor within 24 hours after learning of the event, regardless of relationship to study drug:

- SAEs (defined in Section 5.2.2; see Section 5.4.2 for details on reporting requirements)
- AEs of special interest (defined in Section 5.2.3; see Section 5.4.2 for details on reporting requirements)
- Pregnancies (see Section 5.4.3 for details on reporting requirements)

For SAEs and AESI, the investigator must report new significant follow-up information to the Sponsor immediately (i.e., no more than 24 hours after becoming aware of the information). New significant information includes the following:

- New signs or symptoms or a change in the diagnosis
- Significant new diagnostic test results
- Change in causality based on new information
- Change in the event's outcome, including recovery
- Additional narrative information on the clinical course of the event

Investigators must also comply with local requirements for reporting SAEs to the local health authority and IRB/EC.

5.4.1 Medical Monitors and Emergency Medical Contacts

Investigators will be provided with contact information for the Medical Monitor. To ensure the safety of study patients, an Emergency Medical Call Center will be available

24 hours per day, 7 days per week, in case the above-listed contacts cannot be reached. The Emergency Medical Call Center will connect the investigator with an Emergency Medical Contact, provide medical translation service if necessary, and track all calls. Contact information, including toll-free numbers for the Emergency Medical Call Center, will be distributed to investigators.

5.4.2 Reporting Requirements for Serious Adverse Events and Adverse Events of Special Interest

5.4.2.1 Events That Occur Prior to Study Drug Initiation

After informed consent has been obtained but prior to initiation of study drug, only SAEs caused by a protocol-mandated intervention should be reported. The paper Clinical Trial *Adverse Event/Special Situations* Form provided to investigators should be completed and submitted to the Sponsor or its designee immediately (i.e., no more than 24 hours after learning of the event), either by faxing or by scanning and emailing the form using the fax number or email address provided to investigators.

5.4.2.2 Events That Occur after Study Drug Initiation

After initiation of study drug, SAEs and AESI will be reported until 48 weeks after the final dose of study drug but may be extended in patients whose B cells take longer to replete. Investigators should record all case details that can be gathered immediately (i.e., within 24 hours after learning of the event) on the AE eCRF and submit the report via the electronic data capture (EDC) system. A report will be generated and sent to Roche Safety Risk Management by the EDC system.

In the event that the EDC system is unavailable, the paper Clinical Trial *Adverse Event/Special Situations* Form provided to investigators should be completed and submitted to the Sponsor or its designee immediately (i.e., no more than 24 hours after learning of the event), either by faxing or by scanning and emailing the form using the fax number or email address provided to investigators. Once the EDC system is available, all information will need to be entered and submitted via the EDC system.

Instructions for reporting serious AEs that occur >48 weeks after the final dose of study treatment are provided in Section 5.6.

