3.1.1.2 Double-Blind Treatment Phase

This is an event-driven study. Patients will be treated for a minimum of 120 weeks (with a minimum of five study drug doses, with 24-week follow-up after fifth dose, with each dose 24 weeks apart) or longer and the blinded treatment will continue until at least 205 events of cCDP12 have occurred in the study. The primary efficacy analysis will be

performed after the above-mentioned number of events has been reached (in accordance to the definition of events for the primary estimand). Of note: each study dose period will last for 24 weeks, starting from the study drug dose administration.

Of note: Patients who prematurely discontinue from study treatment, including patients who start receiving an approved MS DMT medication, will remain in the main double-blind study phase and will be followed for both efficacy and safety until the end of the double-blind phase (i.e., until the time of the primary analysis).

Patients *and* investigators will remain blinded to the original (randomized) treatment allocation of patients who discontinued study treatment until the primary analysis is performed and *the decision to start the OLE phase is communicated by the Sponsor*.

A minimum interval of 20 weeks should be kept between the ocrelizumab second infusion of Dose 1 (i.e., infusion Day 15) and the next infusion of Dose 2 (Week 24). A minimum of 22 weeks must occur between ocrelizumab single infusions administered during Weeks 24, 48, 72, 96, and any dose thereafter. *Minimum dosing intervals are to be used in exceptional circumstances only and visits should be scheduled according to the SoA outlined in [Appendix 1](#).*

At infusion visits, patients should remain in observation for at least 1 hour after the completion of the infusion.

Treatment with the first study drug infusion should occur within 24 hours of randomization (in exceptional cases within 48 hours of randomization provided that the investigator assures that all inclusion and exclusion criteria are still met on the day of dosing). If for logistical reasons the ocrelizumab infusion at Week 24, 48, 72, 96, or any further infusion thereafter cannot be administered on the same study visit day, the infusion should be given within the next 24 hours, provided that the patient still meets re-treatment criteria (refer to Section 4.3.2.3). Whenever possible, infusion bags should be prepared on the day of the infusion administration.

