5.3.1 Adverse Event Reporting Period

Investigators will seek information on AEs at each patient contact. All AEs, whether reported by the patient or noted by study personnel, will be recorded in the patient's medical record and on the AE eCRF.

After informed consent has been obtained but prior to initiation of study drug, only SAEs caused by a protocol-mandated intervention (e.g., invasive procedures such as biopsies,

discontinuation of medications) should be reported (see Section 5.4.2 for instructions for reporting serious adverse events).

After initiation of study drug, all AEs will be reported throughout the study duration.

Instructions for reporting AEs that occur after the AE reporting period are provided in Section 5.6.

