5.6 ADVERSE EVENTS THAT OCCUR AFTER THE ADVERSE EVENT REPORTING PERIOD

The Sponsor should be notified if the investigator becomes aware of any serious AE that occurs after the end of the AE reporting period (defined as during the study), if the event is believed to be related to prior study drug treatment. These events should be reported through use of the AE eCRF. However, if the EDC system is not available, the investigator should report these events directly to the Sponsor or its designee, either by faxing or by scanning and emailing the paper Clinical Trial *Adverse Event/Special Situations* Form using the fax number or email address provided to investigators.

5.7 EXPEDITED REPORTING TO HEALTH AUTHORITIES, INVESTIGATORS, INSTITUTIONAL REVIEW BOARDS, AND ETHICS COMMITTEES

Prompt notification (i.e., within 24 hours of awareness) by the investigator to the Sponsor of a serious adverse event is essential so that legal obligations and ethical responsibilities towards the safety of participants and the safety of a study treatment under clinical investigation are met.

The Sponsor has a legal responsibility to notify regulatory authorities about the safety of a study treatment under clinical investigation. The Sponsor will comply with regulatory requirements for expedited safety reporting to regulatory authorities (which includes the use of applicable systems, such as EudraVigilance), Institutional Review Boards or Ethics Committees (IRBs/ECs), and investigators.

Investigator safety reports must be prepared for suspected unexpected serious adverse reactions according to local regulatory requirements and Sponsor policy and forwarded to investigators as necessary.

To determine reporting requirements for single AE cases, the Sponsor will assess the expectedness of these events through use of the reference safety information in the Ocrelizumab Investigator's Brochure.

The Sponsor will compare the severity of each event and the cumulative event frequency reported for the study with the severity and frequency reported in the applicable reference document.

Reporting requirements will also be based on the investigator's assessment of causality and seriousness, with allowance for upgrading by the Sponsor as needed. An iDMC will monitor the incidence of the above-listed anticipated events during the study. An aggregate report of any clinically relevant imbalances that do not favor the test product will be submitted to health authorities.

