- p Patients will receive prophylactic treatment with 100 mg of methylprednisolone (or equivalent) IV and an oral or IV antihistamine (e.g., IV diphenhydramine 50 mg or an equivalent dose of an alternative) prior to infusion of ocrelizumab. The methylprednisolone administration is to be completed approximately 30 minutes before the start of each ocrelizumab infusion; antihistamines should be administered 30–60 minutes prior to the start of an infusion. In the rare case when the use of methylprednisolone is contraindicated for the patient, use of an equivalent dose of an alternative steroid should be used as premedication prior to the infusion. It is also recommended that patients receive an analgesic/antipyretic such as acetaminophen/paracetamol (1 g) prior to ocrelizumab infusion.

- q The investigator must review the clinical and laboratory re-treatment criteria prior to subsequent infusion of ocrelizumab. The patient will need to remain under observation at the clinical site for at least 1 hour after infusion. At infusion visits, it is anticipated that the patient will need to stay at the hospital or clinical site for a full day. Treatment with the first study drug infusion should occur within 24 hours of randomization (in exceptional cases within 48 hours of randomization provided that the Investigator assures that all inclusion and exclusion criteria are still met on the day of dosing). If for logistical reasons the ocrelizumab infusion at Week 24, 48, 72, 96, or any further infusion thereafter cannot be administered on the same study visit day, the infusion should be given within the next 24 hours provided that the patient still meets re treatment criteria. Whenever possible, infusion bags should be prepared on the day of the infusion administration.
- r Medication (e.g., prescription drugs, over-the-counter drugs, vaccines, herbal or homeopathic remedies, nutritional supplements) used by a patient in addition to protocol-mandated treatment.
- s All AEs will be reported for as long as the patient remains in the study. The investigator should follow each AE until the event has resolved to baseline grade or better, the event is assessed as stable by the investigator, the patient is lost to follow up, or the patient withdraws consent. Every effort should be made to follow all serious AEs considered to be related to study drug or trial-related procedures until a final outcome can be reported.

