#### **4.5 SAFETY ANALYSES**

The safety analysis set (SAS) is described in Section 3. All safety parameters will be summarized and presented in tables on the basis of this analysis set. Randomized patients who receive incorrect therapy will be summarized in the group according to the rules laid out in Section 3. Patients who received at least one dose of ocrelizumab above 600 mg will be grouped in the higher dose of ocrelizumab arm.

Patients who are not randomized but who receive study drug will be included in the SAS and summarized according to the therapy actually received.

All patients who received at least one infusion (partial or complete) of study drug with patients grouped according to actual treatment received will be included in the analysis.

- The safety data will be summarized regardless of premature study treatment discontinuation or switch to an approved MS DMT medication (including commercial ocrelizumab).
- Additionally, the safety data may also be summarized regardless of premature study treatment discontinuation but until switching to an approved MS DMT medication (including commercial ocrelizumab).

Safety will be assessed through summaries of exposure to study treatment, AEs, changes in laboratory test results, and changes in vital signs. All verbatim AE terms will be mapped to MedDRA thesaurus terms, and AE severity will be graded according to National Cancer Institute Common Terminology Criteria for Adverse Events (NCI CTCAE) v5.0. All AEs, SAEs, AEs leading to death, AEs of special interest, and AEs leading to study treatment discontinuation that occur on or after the first dose of study treatment (i.e., treatment-emergent AEs) will be summarized by mapped term,

appropriate thesaurus level, and severity grade. For events of varying severity, the highest grade will be used in the summaries. Deaths and cause of death will be summarized. Relevant laboratory and vital sign (pulse rate, and blood pressure) data will be displayed by time, with grades identified where appropriate. Additionally, a shift table of selected laboratory tests will be used to summarize the baseline and maximum post baseline severity grade. Changes in vital signs will be summarized.

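### Protocol 5.4.2.2 stops SAE/AESI reporting 48 weeks after the last dose while 5.3.1, Appendix 1 and 5.6 run it for the whole study, so unrelated late SAEs could go unreported in time that still counts

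*Protocol*

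**What the plan says.** **Reporting period, short version.** Protocol 5.4.2.2: "SAEs and AESI will be reported until 48 weeks after the final dose of study drug but may be extended in patients". The extension is meant for slow B-cell recovery. The section then adds: "Instructions for reporting serious AEs that occur >48 weeks after the final dose of study treatment are provided in Section 5.6".

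**Reporting period, long version.** Protocol 5.3.1: "After initiation of study drug, all AEs will be reported throughout the study duration". Appendix 1, footnote s: "All AEs will be reported for as long as the patient remains in the study".

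**The section to which late events are sent.** Protocol 5.6 sets a duty to notify the sponsor in the following case: "serious AE that occurs after the end of the AE reporting period (defined as during the study), if the event is believed to be related". The relationship meant is with earlier study drug. The section thus carries a relatedness condition and also defines the reporting period as the study.

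**Who is affected.** Under Protocol 3.1.1.2, patients who stop study treatment early "will remain in the main double-blind study phase and will be followed for both efficacy and safety until the end of the double-blind phase".

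**How the SAP uses the data.** SAP 4.5: "The safety data will be summarized regardless of premature study treatment discontinuation or switch to an approved MS DMT medication (including commercial ocrelizumab"). SAP 4.5.1.2 runs duration under observation from first infusion to the latest recorded date before the clinical cutoff, with no limit at 48 weeks after the last dose. SAP 4.5.2 gives rates per 100 patient-years for SAEs, serious infections, opportunistic infections and malignancies, among others.

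**The concern.** The two versions of the reporting period agree while a patient is being dosed. They part for a patient who has stopped treatment, is still in the double-blind phase, and is more than 48 weeks past the last dose. For that patient, 5.3.1 and Appendix 1 require every SAE. Section 5.4.2.2 closes regular reporting and points to 5.6, where only related events are requested. Section 5.4.2.2 is also the place a site would look, because the SAE and AESI definitions (5.2.2, 5.2.3) and the immediate-reporting list (5.4) refer to 5.4.2 for instructions.

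If a site followed 5.4.2.2, unrelated SAEs in that window would be missing from the numerator while the time stayed in the denominator. Rates per 100 patient-years would be too low. Were off-treatment time unequal between arms, the comparison of higher with approved dose would shift as well. The clarification letter of 22 November 2024 does not address the point.

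**Working it through.** There is no figure in the plan to reproduce; the finding rests on the text. The arithmetic only sizes the exposed time.

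**1. The passages side by side**, for an unrelated SAE in a patient still in the double-blind phase, more than 48 weeks after the last dose, with B cells already recovered:

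| Section | Is the SAE to be reported? |
|---|---|
| 5.3.1 | Yes, all AEs |
| Appendix 1, footnote s | Yes, while in the study |
| 5.4 | Yes, whatever the relationship, but refers to 5.4.2 for details |
| 5.4.2.2 | No, period over; go to 5.6 |
| 5.6 | Not requested (unrelated), though by its own definition the period has not ended |

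These cannot all be followed. If B cells have not recovered, 5.4.2.2 says reporting may be extended, not that it must be.

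**2. Single patient.** Exposed weeks = max(0, F − L − 48), where F is weeks of follow-up and L the week of the last infusion. F = 120 is the minimum in SAP 2.3. F ≈ 213 runs from the start of enrolment (SAP 2.2, taken as mid-November 2020) to the cutoff (SAP 2.3, taken as mid-December 2024).

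| Last infusion | F = 120 | F = 213 |
|---|---|---|
| Week 2 | 120 − 2 − 48 = 70 (58%) | 213 − 2 − 48 = 163 (77%) |
| Week 48 | 120 − 48 − 48 = 24 (20%) | 213 − 48 − 48 = 117 (55%) |
| Week 96 | 0 | 213 − 96 − 48 = 69 (32%) |

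**3. Whole trial.** The documents give no rate of stopping treatment while staying in the study, so these are illustrations under stated assumptions.

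- *Fixed share stops but stays.* Assume 798 patients enrolled evenly from November 2020 to December 2021 and 67 from April to August 2022 (SAP 2.2), all followed to mid-December 2024, with the last dose equally likely at any dosing visit. Total time is about 2,994 patient-years, and 34.3% of a stopper's own time is exposed. With 5%, 10% or 20% stopping, the exposed share is 0.05, 0.10 or 0.20 × 34.3% = 1.7%, 3.4% or 6.9% (about 51, 103 or 205 patient-years).
- *Constant annual stopping, all stay.* Assume exponential stopping, doses every 24 weeks, and follow-up uniform over 2.3 to 4.1 years (120 and 213 weeks). Annual probabilities of 3%, 5% and 10% expose 3.0%, 5.0% and 9.8% of person-time.
- *As above, but half leave the study on stopping.* At 5% and 10% per year, the shares fall to 2.6% and 5.3%.

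**4. Worst case for the rate ratio.** Suppose stopping is 5% per year in one arm and 10% in the other, all stoppers stay, every site follows 5.4.2.2, and no late SAE at all is captured. The ratio is then multiplied by (1 − 0.098)/(1 − 0.050) = 0.95, an error of about 5%. If half of the stoppers leave, it is (1 − 0.053)/(1 − 0.026) = 0.97.

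**The case against.** The strongest reply is that collection is governed elsewhere and would still work. Section 5.4.2.2 belongs to the immediate-reporting rules. Sections 5.3 and 5.3.1 put every AE on the AE eCRF with an assessment of seriousness, and SAP 4.5.2 takes its events from those pages. Section 5.4 requires SAEs irrespective of relationship. Appendix 1 marks AE collection at every double-blind visit, and off-treatment patients keep that schedule. Section 5.6 does not, on its own definition, apply to a patient still in the study. SAP 4.5.2 itself expects a last-dose interval of 72 weeks or more. The extension clause matters too: Protocol 5.1.1.1.6 reports a median B-cell repletion time of 72 weeks at 600 mg, so many patients could still be depleted at 48 weeks.

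Most of this stands. It shows that a site reading the protocol as a whole would record everything. It does not remove a rule that says otherwise: the extension is optional, and it does not cover patients whose B cells have recovered.

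A reader might infer that SAE rates are in fact understated, or that the dose comparison is off by 5%. The documents support neither. Nothing shows that any site stopped reporting. The 5% figure needs an assumed twofold difference in stopping, full retention of stoppers, every site following 5.4.2.2, and loss of related SAEs that 5.6 still requests.

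For scale, the 6.9% SAE proportion in Protocol 1.2, taken as over two years (an assumption), gives 2,994 × 0.069/2 ≈ 103 patients with an SAE. Split 2:1, the standard error of the log rate ratio is √(1/69 + 1/34) ≈ 0.21, a 95% interval of about ×/÷ 1.5. A 5% shift is small beside that.

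**Conclusion.** The protocol is wrong as written: this is an internal inconsistency, not a choice of design. Section 5.4.2.2 cannot be followed together with 5.3.1, Appendix 1 footnote s and the definition in 5.6. The consequence is a possible loss of unrelated SAEs more than 48 weeks after the last dose in patients still under observation. Roughly 2% to 10% of person-time is exposed, and that range rests on assumed stopping and retention rates. Bias between arms further requires off-treatment time to differ by arm.

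One link is inferred. The SAP does not expressly say that duration under observation is the patient-years denominator, although SAP 4.5.4 refers to patient-years of observation and no other person-time is defined for these rates. Incidence by number of patients has no person-time denominator but would also miss any unreported event. The point should be corrected, but it does not threaten the safety conclusions on present evidence.

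**What to change.** 1. **Protocol.** Reword 5.4.2.2 to agree with 5.3.1, Appendix 1 and 5.6: SAEs and AESI are reported for as long as the patient remains in the study, including off-treatment time in the double-blind phase. State that the related-only rule in 5.6 begins when the patient leaves the study. A clarification letter like that of November 2024 is enough, and it settles the rule for patients still in safety follow-up or B-cell monitoring.
2. **Data before the cutoff.** The cutoff was scheduled for December 2024 and the current SAP is stamped February 2025, so a letter cannot change what was collected. Query the sites with patients more than 48 weeks past the last dose to confirm that all SAEs were recorded. The cost is one targeted query; these patients are on a 12-weekly visit schedule.
3. **Analysis.** State in the SAP that duration under observation is the rate denominator, if that is intended. If the query finds that late SAEs were not collected, limit both events and person-time in the SAE rates to the period in which they were. This is a small programming change.
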